##### **Method of assessment**

Throughout the study, the same rater (e.g. an attending physician of a given patient, a psychologist, or a medical staff who has been trained in psychologist equivalent) will assess the status of a given patient whenever possible.

#### **6.4.3 J-CGIC (Japanese version of the Clinical global impression of change)**

J-CGIC will be conducted at Visit 2, 3, 4, 6 and 8 (refer [Table 6-1](#)). J-CGIC at premature discontinuation will not be conducted if patient discontinues because of adverse event.

##### **Assessment Items**

The J-CGIC is simple 7 grade investigator's impression scale (1. Markedly improved, 2. Improved, 3. Slightly improved, 4. No change, 5. Slightly aggravated, 6. Aggravated, 7. Markedly aggravated) ([Homma et al, 2000](#)). The J-CGIC is an assessment which requires a clinician to make a judgment of severity or change with minimal guidelines. This rating instrument is based upon the clinician's experience.

##### **Method of assessment**

Throughout the study, the same rater (an attending physician) will assess the status of a given patient.

#### **6.4.4 Quality of Life- Alzheimer's Disease (QOL-AD)**

QOL-AD will be conducted at Visit 2, and 8 (refer [Table 6-1](#)). QOL-AD at premature discontinuation will not be conducted if patient discontinues because of adverse event.

##### **Assessment Items**

QOL-AD is a 13-item questionnaire to assess the quality of life of Alzheimer's patients from the perspectives of patients and their caregivers. It covers several aspects, for example, the perception of health status, mood, functional capacity, personal relationships and leisure, financial situation, and life as a whole ([Logsdon et al, 1999](#)). Each item is quantified using a Likert scale with score one classified as poor, and score four as excellent where total scores range from 13 to 52.

**Method of assessment**

Caregivers complete the measure as a questionnaire about their patients' QOL, while patients complete it in interview format about their own QOL. The form should be handed to the participant, so that he or she may look at it as a rater gives the instructions. Assessment of QOL of a given patient by his/her caregiver should be considered as primary measurement while assessment of QOL of a given patient by his/herself will be recorded as reference. Throughout the study, the same rater (e.g. an attending physician of a given patient, a psychologist, or a medical staff who has been trained in psychologist equivalent) will give the instructions to both caregivers and patients.

**6.4.5 Modified Crichton Scale**

Modified Crichton scale will be conducted at Visit 2, 3, 4, 6 and 8 (refer [Table 6-1](#)). Modified Crichton scale at premature discontinuation will not be conducted if patient discontinues because of adverse event.

**Assessment Items**

The following 7 items will be evaluated by caregiver. Total score is in the 0 to 56 range. Higher score means more severe impairment.

Orientation, Conversation, Cooperation with family and caregiver, Restlessness, Dressing and clothes, Job and social activities/roles, Leisure activities ([Homma 2000](#)).

A higher score means more severe impairment.

**Method of assessment**

The assessment will be performed by caregiver with using the care diary and the results will be recorded on the eCRF.

**6.4.6 Appropriateness of efficacy assessments**

The MMSE is a brief, practical screening test for cognitive dysfunction. It is the most common and simple cognitive scale for AD ([Folstein 1975](#)).

To confirm whether worsening AD symptom is observed after switching from ChE-inhibitors, assessment of J-CGIC is scheduled at every 4-week for the first 2 months and at every 8-week for the rest of the study. J-CGIC is simple 7 grade investigator's impression scale ([Homma 2000](#)).

Modified Crichton Scale is to assess basic activation of daily living, communication functions, and quality of life ([Homma 2000](#)).

Neuropsychiatric Inventory (NPI) is developed to assess neuropsychiatric symptoms and psychopathology of patients with Alzheimer's disease and other neurodegenerative disorders through the use of screening questions ([Cummings et al. 1994](#)). NPI is commonly used in both clinical trials and clinical practices for assessing behavioral and psychological symptoms of dementia.

QOL-AD is a 13-item questionnaire to assess the quality of life of Alzheimer's patients from the perspectives of both patients and their caregivers. It is simple to administer and rating

consistency of score between patients and their caregivers has been validated (Logsdon et al. 2002). In addition, multinational translational version of original QOL-AD including Japanese has been validated (Matsui et al. 2006).

## 6.5 Safety

Safety assessments will consist of monitoring and recording all adverse events (AEs) and serious adverse events (SAEs).

### 6.5.1 Physical examination

Medical examination will be conducted at patient visit. The investigator will check the patient's condition by direct medical examination. Subjective symptoms will be monitored for at length by direct medical interview with the patients. The care diary will be referred in medical examination. Any abnormality recognized as such compared to pre-administration will be recorded as an adverse event.

### 6.5.2 Vital signs

The following items will be measured at patient visit (refer to [Table 6-1](#)).

#### Examination items

Systolic/diastolic blood pressure, pulse rate, body weight

#### Methods of monitoring

Systolic/diastolic blood pressure and pulse rate will be measured in a sitting position. Body weight will be measured.

### 6.5.3 Laboratory evaluations

The following items will be measured at patient visit (refer to [Table 6-1](#)).

#### Laboratory items

Hematology;

Erythrocyte count, leukocyte count, hemoglobin, hematocrit, platelet count.

Blood chemistry;

Total protein, uric acid, ALP, AST, ALT, LDH, cholinesterase, BUN, creatinine, Na, K, Cl, total cholesterol, triglycerides, CPK, albumin, Ca, P, total bilirubin, amylase.

Urinalysis

Glucose, protein, occult blood.

#### Amounts of test samples to be collected as standard guidance

- Hematology: App. 2.0-mL sample of blood will be collected at screening visit and Visit 8 or discontinuation for a total of app. 4.0 mL.

- Blood chemistry: At screening, app. 9.0 mL sample of blood, and app. 4.0 mL blood at Visit 8 or discontinuation will be collected in an AutoSep vacutainer for a total of app. 13 mL.

### **Methods of collection, processing and storage of test samples**

Samples of venous blood will be collected.

After blood sampling, each investigator should follow the blood test procedure of each study site where he/she belongs to.

### **Laboratory measuring these items**

The hematology and blood chemistry tests will be performed by the laboratory measurement described on [\[Appendix 2\]](#).

#### **6.5.3.1 Urinalysis**

- Urinalysis: App. 5-mL sample of urine will be collected at each of 2 points for a total of app. 10 mL
- For urinalysis, each investigator should follow urine sample procedure of each study site where he/she belongs to.

#### **6.5.4 Electrocardiogram (ECG)**

ECG will be measured at patient visit (refer to [Table 6-1](#)).

##### **Assessment items**

Standard 12-lead ECG, ECG readings (heart rate, PR interval, QRS duration, QT interval, QTcB\*, QTcF\*)

\*: These data will be calculated by EDC system, and the calculated data is input to eCRF automatically.

##### **Method of assessment**

ECG will be taken in a supine position after rest.

Clinically significant abnormalities must be recorded on the relevant section of the medical history/Current medical conditions/AE eCRF page as appropriate.

#### **6.5.5 Pregnancy and assessments of fertility**

Please refer to [Section 7.6](#).

#### **6.5.6 Appropriateness of safety measurements**

The safety assessments selected are standard for this indication/patient population.

### **6.6 Other assessments**

#### **Formulation usability questionnaire**

The Formulation usability preference questionnaire will be used to compare the previous oral AD drugs versus the patch in this study and will be completed at Visit 8 (or discontinuation). The caregiver will select one of the following answers (1. Very easy to use, 2. Easy to use, 3. No change, 4. Not easy to use, 5. Not easy to use at all, 6. Unknown). The caregiver answer in the questionnaire should be recorded in eCRF. The reason for the answer should be recorded in eCRF as possible.

### **Treatment compliance**

The status of application of study drug patches will be investigated at every visit between Visit 3 and Visit 8 (or discontinuation).

### **Investigation Items**

The status of application of rivastigmine patches

### **Methods of investigation**

Treatment compliance will be investigated by Physician in one of the following category:

- <25% Poor
- $25 \leq \sim < 50\%$  Average
- $50 \leq \sim < 75\%$  Good
- $75 \leq \sim \leq 100\%$  Very good
- $> 100\%$  Reason to be specified (overdose or misuse)
- In case of over compliance ( $> 100\%$  Reason to be specified, e.g. patients who ran out of their drug due to overuse or misuse), the investigators record the reason (overdose or misuse) separately on eCRF.

The results of treatment compliance should be recorded in eCRF by the interview to either patients or caregivers. "Applied day" is defined as a date when patch has been applied for more than 16 hours.

#### **6.6.1 Resource utilization**

Not applicable.

#### **6.6.2 Pharmacokinetics**

Not applicable.

## **7 Safety monitoring**

### **7.1 Adverse events**

An adverse event (AE) is appearance of worsening of any undesirable sign, symptom or medical condition occurring after starting study treatment, even if the event is not considered to be treatment-related. Study treatment includes the study medication under evaluation given during any phase of the study.

Medical conditions/diseases present before starting study treatment will only be considered AEs if they worsen after starting study treatment. Non-serious AEs occurring before starting study treatment but after signing the informed consent form will be recorded on the Medical History/Current Medical Conditions pages in eCRF. Abnormal laboratory values or test results constitute adverse events only if they induce clinical signs or symptoms, are considered clinically significant or require therapy. The occurrence of adverse events should be sought by non-directive questioning of the patient at each visit during the study. Adverse events also may be detected when they are volunteered by the patient during or between visits or through physical examination, laboratory test, or other assessments. All adverse events which were observed from the first treatment of the drug to the last treatment of the drug must be recorded on the Adverse Events eCRF with the following information:

The severity grade (mild, moderate, severe)

Its relationship to the drug(s) of interest (suspected/not suspected)

Its duration (start and end dates or if continuing at final exam)

Whether it constitutes a serious adverse event (SAE- see [Section 7.2](#) for definition of SAE)

All adverse events should be treated appropriately. Treatment may include one or more of the following: no action taken (i.e. further observation only); the drug dosage adjusted/temporarily interrupted; the drug permanently discontinued due to this adverse event; concomitant medication given; non-drug therapy given; patient hospitalized/patient's hospitalization prolonged. The action taken to treat the AE should be recorded on the AE pages in eCRF.

Once an adverse event is detected, it should be followed until its resolution or until it is judged to be permanent, and assessment should be made at each visit (or more frequently, if necessary) of any changes in severity, the suspected relationship to the drug, the interventions required to treat it, and the outcome.

Information about common side effects already known about the drug can be found in the Package Insert (PI) or will be communicated between PI updates in the form of individual safety report or periodic safety update report and others. This information will be included in the patient informed consent and should be discussed with the patient during the study as needed.

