## **5.6 Study Completion and Discontinuation**

### **5.6.1 Study completion and post-study treatment**

At a minimum, caregivers of the patients who complete this study or discontinue the drug, including those who refuse to return for a final visit, will confirm the onset (or no onset) of a SAE during at least 30 days following the last dose of study drug or at the patient's last visit, and the result should be recorded in the source document & in eCRF.

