### **6           Visit schedule and assessments**

[Table 6-1](#) lists all of the assessments and indicates with an "x" when the visits are performed.

Patients must be seen for all visits on the designated day, or as close to it as possible as allowed "visit window" of "x" days. Missed or rescheduled visits should not lead to automatic discontinuation. Patients who prematurely discontinue the study for any reason should be scheduled for a visit as soon as possible, at which time all of the assessments listed for the final visit will be performed. At this final visit, all drugs should be reconciled for compliance purpose and the adverse event and concomitant medications reconciled on the eCRF.

Patients/subjects will be contacted for safety evaluations during the 30 days following the last administration of study treatment.

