## **7.2      Serious adverse events**

### **7.2.1    Definition of SAE**

An SAE is defined as any adverse event (appearance of (or worsening of any pre-existing) undesirable sign(s), symptom(s) or medical conditions(s) which meets any one of the following criteria:

- is fatal or life-threatening
- results in persistent or significant disability/incapacity
- constitutes a congenital anomaly/birth defect
- requires inpatient hospitalization or prolongation of existing hospitalization, unless hospitalization is for:

- routine treatment or monitoring of the studied indication, not associated with any deterioration in condition
- elective or pre-planned treatment for a pre-existing condition that is unrelated to the indication under study and has not worsened since signing the informed consent
- treatment on an emergency outpatient basis for an event not fulfilling any of the definitions of a SAE given above and not resulting in hospital admission
- social reasons and respite care in the absence of any deterioration in the patient's general condition
- is medically significant, i.e. defined as an event that jeopardizes the patient or may require medical or surgical intervention to prevent one of the outcome listed above e.g. may require treatment on an emergency outpatient basis for an event not fulfilling any of the SAE definition criteria and not resulting in hospitalization.

All malignant neoplasms will be assessed as serious under "medically significant" if other seriousness criteria are not met.

Any suspected transmission via a medicinal product of an infectious agent is also considered a serious adverse reaction.

All AEs (serious and non-serious) are captured on the eCRF, SAEs also require individual reporting to Novartis Drug Safety & Epidemiology department (DS&E) as per [section 7.2.2](#).

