### **7.2.2 SAE reporting**

Each Serious Adverse Event (SAE), regardless of suspected causality, occurring after the patient has provided informed consent and until 30 days after the patient has stopped study participation (defined as time of last dose of drug taken or last visit whichever is later) will be reported by the investigator to Novartis DS&E by FAX within 24 hours of learning of its occurrence, even if it is not felt to be treatment-related.

Information about all SAEs is collected and recorded on the Serious Adverse Event Report Form. The principle investigator must assess the relationship of any SAE to the drug, complete the SAE Report Form, and send the completed, signed form by fax within 24 hours to Novartis Drug Safety and Epidemiology Department. In case of emergency, investigator other than principle investigator or staff can act for it instead of the principle investigator. The telephone and telecopy number of the contact persons in the local department of Clinical -Drug Safety and Epidemiology, specific to the site, are listed in the investigator folder provided to each site. The principle investigator must submit to Novartis monitor the original SAE report. The original copy of the SAE Report Form and the fax confirmation sheet must be kept with the case report form documentation at the study site.

Any SAEs experienced after this 30 day period should only be reported to Novartis DS&E by FAX if the investigator suspects a causal relationship to the drug.

Recurrent episodes, complications, or progression of the initial SAE must be reported as follow-up to the original episode, regardless of when the event occurs. This report must be submitted within 24 hours of the investigator receiving the follow-up information by the principle investigator. An SAE that is considered completely unrelated to a previously reported one should be reported separately as a new event.

Follow-up information is sent to the same person to whom the original SAE Report Form was sent, using a new SAE Report Form stating that this is a follow-up to the previously reported SAE and giving the date of the original report by FAX. The follow-up information should describe whether the event has resolved or continues, if and how it was treated, and whether the patient continued or withdrew from study participation.

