2.6.2.1 Adverse events (AEs)

All adverse events starting on or after the first treatment will be included in all summaries and will also be listed. Adverse events occurring after signing of the informed consent prior to the start of study treatment will be listed only.

These adverse events will also be summarized by overall, by study periods as Week 1 to Week 4, Week 4 to Week 8, Week 8 to Week 12, Week 12 to Week 16, Week 16 to Week 20 and Week 20 to Week 24 by the following variables.

Adverse events by SOC and PT

All adverse events starting on or after the first treatment will be coded utilizing the MedDRA dictionary, tabulated, and analyzed by primary system organ class and preferred term.

Primary system organ classes will be sorted alphabetically and, within each primary system organ class, the preferred terms will be sorted in descending order of frequency.

If a patient reported more than one adverse event with the same preferred term, the adverse event will be counted only once. If a patient reported more than one adverse event within the

same primary system organ class, the patient will be counted only once at the system organ class level.

AEs by severity

All adverse events will be summarized by maximum severity, primary system organ class and preferred term. If a patient reports more than one adverse event within the same primary system organ class, only one adverse event will be counted for that patient at the highest severity level in the total row for each primary system organ class. If a patient reported more than one adverse event with the same preferred term, the highest (maximum) severity will be presented. Missing severity will be assumed to be severe in the summary table.

AEs suspected to be related to study drug

The treatment emergent adverse events suspected to be related to study drug (according to the investigators) will be summarized by primary system organ class and preferred term. Relationship to study drug is considered as suspected for those events where "Relationship to study drug" is answered by the investigator as "Suspected".

AEs leading to permanent study drug discontinuation

Treatment emergent adverse events leading to permanent study drug discontinuation, regardless of study drug relationship, will be summarized by primary system organ class and preferred term.

AEs requiring dose adjustment or interruption

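### Protocol 7.1 ends the required adverse-event recording at the last treatment, in conflict with the exit visit and the 30-day safety contact, so non-serious events found there may go unrecorded as adverse events

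*Protocol*

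**What the plan says.** Protocol 7.1 sets the recording rule for the adverse-event page: "All adverse events which were observed from the first treatment of the drug to the last treatment of the drug must be recorded". Its definition of an adverse event, in the same section, has a start but no end: a "medical condition occurring after starting study treatment, even if the event is not considered to be treatment-related".

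Other parts of the protocol carry no such cut-off:

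- Section 7.2.1: "All AEs (serious and non-serious) are captured on the eCRF".
- Section 6 and Table 6-1 have adverse events assessed at Visit 8/discontinuation and reconciled on the eCRF at the final visit.
- Section 6.5.1 has abnormalities found at medical examination recorded as adverse events.
- Section 6.5.4 sends clinically significant ECG abnormalities to the history or adverse-event pages.
- Section 6 also states: "Patients/subjects will be contacted for safety evaluations during the 30 days following the last administration of study treatment".

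Serious events have their own rule. Section 7.2.2 has them reported "until 30 days after the patient has stopped study participation (defined as time of last dose of drug taken or last visit whichever is later". Section 5.6.1 sets a minimum check, in which caregivers "will confirm the onset (or no onset) of a SAE during at least 30 days following the last dose of study drug", with the alternative of the patient's last visit.

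On analysis, SAP 2.6.2.1 says: "All adverse events starting on or after the first treatment will be included in all summaries and will also be listed". It gives no end date.

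**The concern.** Some safety information arrives after the last patch. A patient who stops early has the exit visit promptly afterwards, with no visit window (Table 6-1, footnote h). That visit holds the only scheduled post-baseline laboratory tests and ECG. The 30-day contact follows the last administration for everyone. The 7.1 sentence turns on when an event is observed, not when it starts. Read literally, even an event that began on drug but was first seen at a late exit visit falls outside it.

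Safety and tolerability is a secondary objective, and the SAP names gastrointestinal and skin events as of special interest. A non-serious skin reaction has no scheduled data source other than the adverse-event record. Sites that follow 7.1 and sites that follow Section 6 or 7.2.1 would record different events. Serious and non-serious events would also enter the same SAP summaries after being collected over different periods.

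**Working it through.** The point rests on wording, so the main check sets the periods side by side.

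| Source | Governs | Ends |
|---|---|---|
| Protocol 7.1, recording sentence | Adverse-event page | Last treatment + 0 days |
| Protocol 7.1, definition | What counts as an adverse event | No end stated |
| Protocol 7.2.1 | eCRF capture, serious and non-serious | No end stated |
| Protocol 6, Table 6-1 | Assessment and reconciliation | Visit 8/discontinuation |
| Protocol 6 | Safety contact | Last administration + 30 days |
| Protocol 5.6.1 | Minimum serious-event check | Last dose + at least 30 days, or last visit |
| Protocol 7.2.2 | Serious-event reporting | Later of last dose or last visit, + 30 days |
| SAP 2.6.2.1 | Summaries and listings | No end stated; period tables stop at Week 24 |

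**Gap between serious and non-serious events.** Let the last visit fall *d* days after the last dose (*d* ≥ 0). Serious events are reported to last dose + *d* + 30. Under the literal 7.1 rule, non-serious events stop at last dose + 0. The difference is 30 + *d* days: 30 for a patient whose last dose and last visit coincide, and more for one who stays in the study off drug, as Section 5.6.2 provides.

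**Who has an exit visit after the last patch.** For completers, the maintenance phase ends on Day 168 (Section 3.1), which is also the nominal day of Visit 8. The visit window runs from Day 161 to Day 182, and the documents do not say whether patches continue until the visit. The exit-visit part of the point therefore rests on early stoppers. The 30-day contact part applies to all patients.

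**Scale.**

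- Input: 16 of 107 patients in the 1-step arm of study 1303 stopped for an adverse event (Protocol 1.1 and 3.6). 16/107 = 14.95%, which reproduces the stated 15.0%.
- Planned enrolment is 120 (Protocol 9.8). 120 × 16/107 = 17.9, about 18 patients.
- The exact 95% interval for 16/107 is 8.8% to 23.1%. Multiplied by 120, this is about 11 to 28 patients.
- The plan's allowance for non-evaluable patients is 120 − 97 = 23, and 23/120 = 19.2%. That allowance concerns MMSE evaluability and may include patients with no exit visit, so it is only a loose cross-check.

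**What the SAP reports without an adverse-event record.** SAP 2.7.1 gives haematology and chemistry change at Week 24 and lists liver abnormalities at any post-baseline time. SAP 2.7.2.1.2 includes premature-discontinuation visits in the notable vital signs. SAP 2.7.3 summarises and lists ECG values. None of these supplies severity, causality, action taken or outcome.

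**The case against.** The strongest reply is that the 7.1 sentence says what must be recorded and does not forbid recording more. The same section tells sites to ask about adverse events at each study visit and accepts that laboratory tests may reveal them; the only scheduled post-baseline tests are at the exit visit. With Table 6-1 and Sections 6, 6.5.1, 6.5.4 and 7.2.1, many sites would record what they find there. This stands, and it makes the defect a contradiction rather than a settled exclusion. It does not remove the defect, because 7.1 is the only stated period and no passage says whether non-serious events from the 30-day contact are recorded.

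Four stronger readings are tempting, and the documents do not support them:

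- *Events found at exit are left out of the safety results.* The SAP sets no upper cut-off, so any recorded event is summarised. Laboratory, ECG and vital-sign values are reported in their own right.
- *The exit tests always come after the last patch.* For completers the two share a nominal day.
- *About 18 or 23 patients' events are lost.* These figures count patients. The event that caused stopping would ordinarily precede the last patch and be recorded; what is at risk is new events found later.
- *The phrase "following the last dose of study drug or at the patient's last visit" in Section 5.6.1 lets serious-event reporting end with no off-drug period.* That section sets a minimum check. Section 7.2.2, with its later-of rule, is the operative reporting rule.

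It is also fair to say that no passage requires non-serious events to be collected for 30 days. Whether to do so is the sponsor's choice, but the choice should be stated.

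**Conclusion.** The point holds as an internal contradiction with a risk of under-recording. The one stated recording period ends at the last treatment, while the exit visit (for early stoppers) and the 30-day contact (for everyone) come later. Non-serious events found there may go unrecorded as adverse events, depending on which passage a site follows. Serious events are covered for at least 30 days longer, and the SAP gives no end date that would align the two.

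The number of events affected cannot be derived from the documents. The figure of about 18 of 120 (range about 11 to 28) assumes that this trial's patients stop for adverse events at the study 1303 1-step rate. It shows only how many patients would probably have an exit visit after the last patch for that reason. The change is worth making because it corrects a conflict that bears on a secondary objective and needs no new visit.

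**What to change.** 1. In Protocol 7.1, replace the last-treatment cut-off with a recording period that runs at least through the Visit 8/discontinuation visit. State explicitly whether non-serious events reported at the existing 30-day contact are recorded.
2. Reconcile Protocol 5.6.1 and Section 6 with the serious-event window in 7.2.2 (later of last dose or last visit, plus 30 days). Deleting the last-visit phrase from 5.6.1 would not be enough: 5.6.1 and Section 6 would still count from the last dose and so differ from 7.2.2 for patients who remain in the study off drug.
3. In SAP 2.6.2.1, state the matching end date and show events that start after the last patch separately.

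The cost is a protocol amendment and a SAP edit, with no new visit or procedure. Adverse-event counts may rise slightly. Sites will have a few more events to record, and to follow to resolution as 7.1 requires.
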